3. STUDY OBJECTIVES

The objective of this study will be to assess the efficacy and safety of Miconazole oil compared to a placebo oil vehicle when applied twice daily (BID) for 14 days in subjects with otomycosis. Descriptively compare the efficacy and safety of miconazole oil over treatment durations of 7 versus 14 days.

4. STUDY DESIGN

4.1. Overall Study Design

This study is a randomized, partially blinded, multiple-dose, parallel-group design study conducted at up to 10 study centers in the US. Approximately 75 male or female subjects with otomycosis will receive study drug. Subjects will be randomly assigned in a 1:1:1 ratio to receive miconazole oil [administered as 5 drops per ear at \sim 30 mg per drop instilled into the external ear canal of the ear(s) affected by otomycosis] for 7 or 14 days, or vehicle for 14 days. Interim assessments are planned to ensure that there is a sufficient number of subjects within each group for the primary analysis. If deemed necessary the randomization ratio may be adjusted following the interim assessments, see section 6.1.6 for details. For subjects assigned to the 14-day treatment duration with either miconazole oil or vehicle, the contents of the study drug will be blinded to both the subject and the investigator and study staff (i.e., double-blind), but the treatment duration assigned to each subject (7 or 14 days) will be unblinded to both the subject and the investigator and study staff.

At Screening/Baseline (Day 1), the subject will then begin treatment with study drug. All subjects will return to the clinic on Day 8. For subjects randomized to the 7-day treatment duration, this visit will constitute the End of Treatment Visit. Subjects randomized to the 7-day treatment duration will not administer study drug on the day of this visit. All other subjects will

continue to administer the study drug twice per day, up through Day 14, following the same instructions as provided at the Screening/Baseline Visit on Day 1.

All subjects will return to the clinic on Day 15. For subjects randomized to the 7-day treatment duration, this visit will constitute the Test of Cure Visit. For subjects randomized to the 14-day treatment duration, this visit will constitute the End of Treatment Visit. Subjects randomized to the 14-day treatment duration will not administer study drug on the day of this visit. Subjects randomized to the 14-day durations will return to the clinic on Day 22 for the Test of Cure Visit.

Efficacy assessments will include fungal culture of the affected ear(s), assessments of clinical signs and symptoms of otomycosis, and a subject global assessment. In cases of bilateral otomycosis, both ears will be treated and evaluated by the investigator, but the ear with the worse infection at Screening/Baseline, as assessed by the investigator by taking into account both clinical signs and symptoms and fungal culture results, will be used as the study ear for efficacy analyses. If both ears are determined by the investigator to have the same degree of infection at Screening/Baseline, the left ear will be used as the study ear for the purposes of efficacy analyses.

Safety assessments will include AEs.

4.1.1. Schedule of Visits and Assessments

The study schedule can be found in Section 6.1 of the protocol.

4.1.2. Method of Assigning Subjects to Treatment Groups

A randomization schedule will be generated in SAS® using PROC PLAN by a member in the QST Consultations, Ltd. (QST) Statistical Services department who is not associated with the conduct or analysis of the study. The randomization schedule will be stratified by site and separate lists will be produced for each site. Sites will receive sequentially numbered kits randomized in blocks of six in a 1:1:1 ratio.

At the Baseline/Day 1 visit, qualified subjects will be assigned to the lowest numerically available kit at the time of randomization. The assignment of the lowest numerically available kit number must be strictly adhered to as it is the method of randomization for this study. The kit number will be recorded in the electronic case report form (eCRF). Subjects will be randomized in a 1:1:1 ratio to one of three groups: 1) 7-day treatment with miconazole oil; 2) 14-day treatment with miconazole oil; or 3) 14-day treatment with miconazole oil vehicle.

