### 3 STUDY DESIGN

This study is a randomized, partially masked, multiple-dose, parallel-group design study conducted at up to 10 study centers in the US. Approximately 75 male or female subjects with otomycosis will receive study drug. Subjects will be randomly assigned in a 1:1:1 ratio to receive miconazole oil [administered as 5 drops per ear at ~30 mg per drop instilled into the external ear canal of the ear(s) affected by otomycosis] for 7 or 14 days, or vehicle for 14 days. Interim assessments are planned to ensure that there is a sufficient number of subjects within each group for the primary analysis. If deemed necessary the randomization ratio may be adjusted following the interim assessments; see [Section 10.5.5](#) for details. For subjects assigned to the 14-day treatment duration with either miconazole oil or vehicle, the contents of the study drug will be masked to both the subject and the investigator and study staff (i.e., double-blind), but the treatment duration assigned to each subject (7 or 14 days) will be unmasked to both the subject and the investigator and study staff.

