### **3.1 Number of Subjects**

Approximately 75 eligible subjects are planned to be enrolled in order to achieve approximately 10 subjects per group (randomized in a 1:1:1 ratio to the 7-day active, 14-day active, and 14-day vehicle treatment groups) with a positive fungal culture at baseline and who have completed the Test of Cure Visit.

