## 4 STUDY SUBJECTS

### 4.1 Inclusion Criteria

In order to be eligible for the study, subjects must meet all of the following criteria:

1. Male or non-pregnant, non-lactating females
2. Diagnosis of uncomplicated otomycosis of the external ear only, in the ear(s) that will be treated with study drug, with a score for fungal elements of  $>0$  in each ear to be treated with study drug (see [Section 7.4](#) for definitions of the scores for each of the otomycosis signs and symptoms). Subjects must also have at least two of the following signs or symptoms of otomycosis in each ear to be treated with study drug: pruritus,  $>1$ ; debris,  $>1$ ; or pain,  $>0$ .
3. General good health as determined by medical examination and medical history, and who are free of clinically significant disease, including diabetes mellitus that is not well-controlled or that could interfere with the study
4. Females of childbearing potential must have had a negative urine pregnancy test at Screening/Baseline and must agree to use an effective method of contraception (as defined in [Section 8.5](#)) from Screening/Baseline up through the Test of Cure Visit (see [Section 6](#)). Females of childbearing potential include any female who has experienced menarche and who has not undergone successful surgical sterilization (hysterectomy, bilateral tubal ligation or bilateral oophorectomy) or is not postmenopausal (defined as amenorrhea  $>12$  consecutive months). Females who are using oral, implanted, or injectable contraceptive hormones, an intrauterine device (IUD), barrier methods (diaphragm, condoms, spermicide) to prevent pregnancy, practicing abstinence or where partner is sterile (e.g., vasectomy), should be considered to be of childbearing potential
5. Subjects and/or their caregivers (as appropriate for the age of the subject) must have full legal capacity to volunteer
6. Subjects and/or their caregivers must have completed an appropriately administered institutional review board (IRB)-approved informed consent and assent (as applicable) prior to any study related procedures
7. Subjects and their caregivers (as applicable) must agree to comply with all requirements of the protocol

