4.1.3. Blinding

The Sponsor, the clinical research organization, the investigator, study site personnel and subjects will be blinded to the treatment assignment if the subject is randomized to a 14-day treatment group. Otherwise subjects in the 7 day treatment group will unblinded. The randomization schedule will be kept strictly confidential and accessible only to authorized persons. Only when the study has been completed, the populations determined, and the study database locked will the randomization schedule be made available for analysis.

The integrity of this clinical study must be maintained by observing the treatment blind. If an adverse event occurs which cannot be managed without knowing whether the subject is receiving active study drug or vehicle solution, the investigator should contact the unblinded sponsor staff to obtain treatment assignment information. The Medical Monitor must be notified whenever study medication is unblinded, preferably prior to unblinding a subject. The duration of treatment will not be blinded. For subjects randomized to the 14-day treatment durations, the contents of the study drug (miconazole oil versus vehicle) will be blinded. Randomized study drug will be packaged in identical bottles and will be labeled with a randomization number rather than the contents of the bottle.

For subjects randomized to the 14-day durations, if it becomes necessary to unblind a subject's treatment assignment in case of emergency, the investigator should contact the unblinded sponsor staff. A person at the sponsor organization who is not otherwise involved with the study will maintain a randomization list that will enable that person to inform the investigator of the subject's treatment allocation. The treatment allocation is to be obtained only if a medical emergency exists and knowledge of the medication being taken will influence the medical management of the subject.

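### One fixed block size of six within each site, with treatment duration open, makes some next durations predictable and exposes the descriptive 7-versus-14-day comparison to selection bias

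*SAP*

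**What the plan says.** SAP 4.1.2 sets the allocation method: "The randomization schedule will be stratified by site and separate lists will be produced for each site", and "Sites will receive sequentially numbered kits randomized in blocks of six in a 1:1:1 ratio". At 1:1:1 each block holds two 7-day active, two 14-day active and two 14-day vehicle kits, that is, two 7-day and four 14-day. Dispensing follows kit order: "qualified subjects will be assigned to the lowest numerically available kit at the time of randomization".

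Duration is open. Protocol Section 3 says "the treatment duration assigned to each subject (7 or 14 days) will be unmasked to both the subject and the investigator and study staff", and SAP 4.1.3 says "The duration of treatment will not be blinded". Masking covers only the 14-day arms, where "the contents of the study drug (miconazole oil versus vehicle) will be blinded".

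Eligibility is settled before randomization (Protocol 6.2.1) and rests partly on scores the investigator assigns: "Subjects must also have at least two of the following signs or symptoms of otomycosis in each ear to be treated with study drug" (Protocol 4.1, criterion 2).

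Protocol 9.2 gives the 1:1:1 ratio but no block size; the figure six appears only in the SAP. SAP 4.1.3 keeps the schedule confidential but does not mention the block size. Neither document describes varying block sizes or central allocation.

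**The concern.** Foreseeing the end of a block does not require sight of the schedule. It requires the block size and the durations already assigned at that site, and the second is open. Once both 7-day kits of a block are gone, the rest of the block is 14-day. Once all four 14-day kits are gone, the rest is 7-day.

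The person who can foresee the next duration may also score the signs that determine eligibility and influence when a patient is enrolled. Bringing milder or more severe patients forward for a known duration would shift prognosis between the duration arms. Comparing 7 with 14 days is a stated objective (Protocol Section 2). It is reported as unadjusted percentages by arm; SAP 6.1.4 and 6.1.7 mark covariate adjustment and multicenter considerations as not applicable. Since no hypothesis is tested, what is at stake is a distorted estimate, not a type I error.

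**Working it through.** The plan gives no predictability figure to reproduce, and its sample size is stated not to rest on statistical considerations.

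**Inputs.** Blocks of six with two 7-day and four 14-day kits, site lists and kit order (SAP 4.1.2); open duration (Protocol 3, SAP 4.1.3); about 75 subjects (Protocol 3.1); up to 10 sites (Protocol 3.2). Assumption for this step: the observer knows the block size.

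**Complete block.** There are C(6,2) = 15 equally likely duration patterns. A position is certain when all kits remaining in the block have the same duration.

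| Position | Certain 14-day | Certain 7-day | Total |
|---|---|---|---|
| 1, 2 | 0 | 0 | 0 |
| 3 | 1/15 | 0 | 1/15 |
| 4 | 3/15 | 0 | 3/15 |
| 5 | 6/15 | 1/15 | 7/15 |
| 6 | 10/15 | 5/15 | 15/15 |
| Sum | 20/15 | 6/15 | 26/15 |

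- Share certain: (26/15)/6 = 28.9%.
- By arm: (6/15)/2 = 20.0% of 7-day and (20/15)/4 = 33.3% of 14-day assignments.
- Best-guess accuracy for duration is 74.4%, against 66.7% from always guessing 14-day.

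**Realistic site sizes.** Positions 7 and 8 open a new block and are never certain.

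- 7 subjects: (26/15)/7 = 24.8%. 8 subjects: (26/15)/8 = 21.7%.
- 75 subjects over 10 sites (five of 7, five of 8): 10 × 26/15 = 17.3, and 17.3/75 = 23.1%, if 1:1:1 ran throughout.
- Equal splits over 1 to 10 sites: 20.0% to 27.8%. A site with 5 subjects: (11/15)/5 = 14.7%.

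**Can a small site infer the block size?** At 7-8 subjects every certain position lies in the first block, before the site has seen a complete one. Exactly two 7-day kits among the first six has probability 1.0 under blocks of 3, 0.54 under 9, 0.45 under 12 and 0.33 under simple randomization, so one block could not settle it anyway.

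**Upper bound on bias.** Let delta be the shift in cure probability when a site acts on a certain prediction. It is assumed; the documents give no value. If every certain prediction is acted on, in opposite directions for the two durations, bias = delta × (certain share of 7-day + certain share of 14-day).

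- Complete blocks: 0.200 + 0.333 = 0.533. Delta 0.10 gives 5.3 points; 0.20 gives 10.7.
- 8 subjects per site: 0.4/2.667 + 1.333/5.333 = 0.15 + 0.25 = 0.40. Delta 0.10 gives 4.0 points; 0.20 gives 8.0.

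**Alternatives.** In simulations where the observer knows the set of sizes but not their order, random sizes 3/6/9 leave 1.4% certain at 7 subjects per site, 2.0% at 8, 2.9% at 12 and 3.2% at 18. A larger fixed block helps much less: in complete blocks, 21.4% for nine and 17.0% for twelve. With 75 subjects over 10 sites, the simulated chance that the two 14-day arms differ by 6 or more is about 6% for fixed six, 7% for 3/6/9 and 12% for 6/9/12.

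**The case against.** The strongest reply is that certainty presupposes something the documents never say sites have. The block size is only in the SAP, the schedule is confidential, and Protocol 9.4.1 mentions a separate randomization plan that may deal with disclosure. This stands. A reader might infer that site staff will in fact know 22-29% of durations in advance. The documents do not support that: the figures hold only for someone who already knows the block size or has worked it out, and working it out is plausible only at larger sites after the first block. They do not show that the size is withheld either.

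Second, the 4-11 points could be read as an expected bias. They are a worst case on an assumed delta. Screening, randomization and first dose share one Day 1 visit, which limits the room for manoeuvre. Baseline signs and symptoms are tabulated by arm (SAP 6.5, Tables 14.1.2.1 and 14.1.2.2), so a shift in them would be visible, though not adjusted for.

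Third, precision is low in any case: "Approximately 75 eligible subjects are planned to be enrolled in order to achieve approximately 10 subjects per group". With 10 per arm and cure near 50%, the 95% half-width for a difference is 1.96 × √(2 × 0.25/10) = 0.44, or 44 points. That limits the weight of the point, but a systematic error is not removed by noting a large random one.

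Fourth, one might suppose that the assessment in SAP 6.1.6 restores balance between durations. It does not: it withdraws 7-day kits and rebalances only the two 14-day arms.

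**Conclusion.** The point holds as a conditional weakness of design. For anyone who knows the block size, up to 28.9% of durations are certain in advance in complete blocks, and about 22-25% at 7-8 subjects per site. Those shares follow from SAP 4.1.2 by enumeration. Whether anyone at a site has that knowledge, and whether anyone would act on it, the documents do not say. The bias is therefore unknown, with an upper bound of about 4-11 points under delta of 0.10-0.20.

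Only the descriptive 7-versus-14-day comparison is exposed. It would be wrong to extend the concern to active versus vehicle within 14 days, because masked contents cannot be deduced from past durations.

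The shares apply only while 7-day kits remain in the schedule. After withdrawal under SAP 6.1.6, every later duration is known. A better method costs little and serves a stated objective, so the change is worth making where it can still take effect.

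**What to change.** In SAP 4.1.2, for every schedule extension or new site list that still contains 7-day kits, replace the fixed block of six with permuted blocks whose sizes are drawn at random from 3, 6 and 9 at 1:1:1. State that block sizes are withheld from sites and blinded personnel. Keep PROC PLAN, the site lists and lowest-kit dispensing. Adding a block of 12 in place of 3 is less attractive because of the imbalance figures above.

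The cost is a few lines of code and a sentence or two in the SAP and the randomization plan, plus the small rise in 14-day imbalance from about 6% to 7%.

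The reach is limited. The change does nothing for kits already shipped or once 7-day kits are withdrawn. The SAP is dated 30 May 2019, and the May 2018 amendment already cites a lower than planned rate of culture-positive completers, so enrolment was under way and few 7-day kits may remain to be scheduled.

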4.1.3. Blinding

The Sponsor, the clinical research organization, the investigator, study site personnel and subjects will be blinded to the treatment assignment if the subject is randomized to a 14-day treatment group. Otherwise subjects in the 7 day treatment group will unblinded. The randomization schedule will be kept strictly confidential and accessible only to authorized persons. Only when the study has been completed, the populations determined, and the study database locked will the randomization schedule be made available for analysis.

The integrity of this clinical study must be maintained by observing the treatment blind. If an adverse event occurs which cannot be managed without knowing whether the subject is receiving active study drug or vehicle solution, the investigator should contact the unblinded sponsor staff to obtain treatment assignment information. The Medical Monitor must be notified whenever study medication is unblinded, preferably prior to unblinding a subject. The duration of treatment will not be blinded. For subjects randomized to the 14-day treatment durations, the contents of the study drug (miconazole oil versus vehicle) will be blinded. Randomized study drug will be packaged in identical bottles and will be labeled with a randomization number rather than the contents of the bottle.

For subjects randomized to the 14-day durations, if it becomes necessary to unblind a subject's treatment assignment in case of emergency, the investigator should contact the unblinded sponsor staff. A person at the sponsor organization who is not otherwise involved with the study will maintain a randomization list that will enable that person to inform the investigator of the subject's treatment allocation. The treatment allocation is to be obtained only if a medical emergency exists and knowledge of the medication being taken will influence the medical management of the subject.

5. EFFICACY AND SAFETY ENDPOINTS

5.1. Efficacy Endpoints

The primary and secondary endpoints will be based on the investigator reporting of signs and symptoms for the study ear. Other efficacy endpoints will be based on the subject reporting of the symptom of pruritus.

5.1.1. Primary Efficacy Endpoints

The primary efficacy endpoint is

- The percentage of subjects at the Test of Cure Visit with "therapeutic cure," defined as a negative mycological [fungal] culture plus "clinical cure" for the study ear. Clinical cure

is defined as the absence of all otomycosis signs and symptoms based on Investigator assessment according to the scales for each individual sign or symptom and with absence defined as a score of 0 on each of the scales for pruritus, debris, fungal elements, and pain.

5.1.2. Secondary Efficacy Endpoints

The secondary efficacy endpoints are as follows:

- Percentage of subjects with clinical cure at the Test of Cure Visit
- Percentage of subjects with a negative fungal culture at the Test of Cure Visit
- Percentage of subjects with a negative fungal culture at the Test of Cure visit as well as individual sign or symptom score of 0 or 1 on each of the scales for pruritus and debris and a score of 0 on each of the scales for fungal elements and pain.
- Percentage of subjects with individual signs or symptoms with a score of 0 or 1 on each of the scales for pruritus and debris and a score of 0 on each of the scales for fungal elements and pain.
- Subject global assessments at Baseline and Test of Cure as well as categorical shifts in the subject global assessment scale scores from the Screening/Baseline to the Test of Cure Visit.

Analyses may also be conducted by fungal organism isolated at Screening/Baseline if a common organism is isolated by at least 5 subjects.

5.1.3. Additional Efficacy Endpoints

Other efficacy endpoints based on subject reporting of pruritus will include the following:

- Subject therapeutic cure (defined as a negative mycological culture plus clinical cure) at the Test of Cure Visit for the study ear based on subject assessment of pruritus. Clinical cure is defined as the absence of all otomycosis signs and symptoms according to the scales for each individual sign or symptom and with absence defined as a score of 0 on each of the scales for pruritus, debris, fungal elements, and pain.

5.2. Safety Endpoints

Safety endpoints will be the percentage of subjects with treatment-emergent AEs, with treatment-emergent defined as occurring upon or after administration of the first dose of study drug.

6. STATISTICAL AND ANALYTICAL PLANS

6.1. General Methodology

All statistical processing will be performed using SAS® unless otherwise stated. No interim analyses are planned.

No formal hypotheses will be tested in this study. Descriptive comparisons will be made between the micronazole oil and the oil vehicle groups for subjects randomized to the 14-day groups. Additionally, descriptive comparisons will be made between the 7-day and 14-day groups for subject's randomized to the miconazole oil treatment.

Descriptive statistics will be used to provide an overview of the efficacy and safety results. For categorical parameters, the number and percentage of subjects in each category will be presented. For continuous parameters, descriptive statistics will include n (number of subjects), mean, standard deviation (SD), median, minimum, and maximum.

The primary method of handling missing efficacy data will be the method of last observation carried forward (LOCF) imputation.

